11.4 Secondary endpoints and analyses

OS, local/regional control, and disease control will be estimated using the Kaplan-Meier method and compared between arms using log-rank tests and Cox regression models. Fisher's exact test will be used to compare the number of pembrolizumab (MK-3475) doses received by participants on each treatment arm. Pathologic response, RECIST 1.1

response rates, iRECIST response rates will be tabulated for the neoadjuvant arm and exact 95% confidence intervals will be constructed. For each arm, 250 participants will be sufficient to estimate toxicity to within $\pm 6\%$. Any toxicity occurring with at least 1% probability is likely to be seen at least once (99% probability).

Primary analyses will all be intent-to-treat. We will perform additional analyses per protocol, to understand how variation in treatment in the neoadjuvant arm can impact the analyses.

CLOSED EFFECTIVE 05/05/2022

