1.0 OBJECTIVES

- 1.1 Primary Objective(s)
 - a. To compare event-free survival (EFS) in participants with high-risk resectable melanoma randomized to neoadjuvant pembrolizumab (MK-3475) with participants randomized to adjuvant pembrolizumab (MK-3475).
- 1.2 Secondary Objective(s)
 - a. To assess the frequency and severity of toxicities on each of the arms.
 - b. To compare between arms overall survival (OS), disease control at 24 weeks, locoregional control in the surgical site(s), and total number of pembrolizumab (MK-3475) doses received.
 - c. On the neoadjuvant arm, to estimate the pathologic response rate, the RECIST 1.1 response rate (confirmed and unconfirmed CR and PR), and the iRECIST response rate (confirmed and unconfirmed CR and PR), before surgical resection; to compare definitions of pathologic partial response; and to evaluate the association between pathologic response and EFS and OS.
 - d. To describe the proportion of participants on each arm who received the surgery planned at randomization.
- 1.3 Additional Objective(s)
 - a. To bank tumor tissue and whole blood in anticipation of future correlative studies in this participant population. Such proposed analysis includes deep immune profiling, with evaluation of CD3, CD8, PD-L1, CD20, whole exome sequencing studies, and RNA analysis.

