7.2 Treatment

a. Pre- pembrolizumab (MK-3475) Labs

Blood collected for pretreatment laboratory tests must be collected and analyzed no more than 3 days prior to dosing.

b. Surgery

Participants must undergo surgical resection (lymphadenectomy or resection of in-transit or distant metastasis +/- wide local excision, if applicable) of clinically detectable melanoma. **Timing of surgery is dependent on treatment arm.**

For all participants, the **S1801 Planned Surgery Form** must be filled out prior to randomization and the **S1801 Post-Surgery Form** filled out post-surgery. Submit forms as indicated in [Section 14.0](#).

Pembrolizumab (MK-3475) timing after surgery is up to the discretion of the local investigator. Interval between surgery and start of adjuvant therapy should not exceed 84 days.

c. **Arm 1: Pembrolizumab (MK-3475) Adjuvant Arm**

Step 1: RANDOMIZATION

Participants will be randomized.

Step 2: SURGERY

Participants on Adjuvant arm must be registered to Step 2 (Surgery) within 17 days (preferably within 14 days) after randomization and must undergo surgical resection within 17 days (preferably within 14 days) after Step 2 registration. Radiation is allowed after surgery. **However, interval between Surgery and the start of Adjuvant therapy must not exceed 84 days.**

Step 3: ADJUVANT THERAPY

It is recommended that participants be registered to and initiate treatment on Step 3 (Adjuvant therapy) within 17 days (preferably within 14 days) after surgery. Radiation is allowed after surgery. However, interval between Surgery and start of Adjuvant therapy must not exceed 84 days.

Agent	Dose	Schedule	Route
MK-3475 (pembrolizumab)	200 mg	IV over 30 minutes	Day 1, Q 3 weeks for 18 doses

Pembrolizumab (MK-3475) treatment should be administered after all procedures and assessments have been completed. Pembrolizumab (MK-3475) treatment may be administered up to 3 days before or after the protocol-specified Q 3 weeks due to administrative reasons.

Pembrolizumab (MK-3475) treatment will be administered on an outpatient basis.

Pembrolizumab (MK-3475) will be administered as a 30-minute IV infusion. Infusion timing should be as close to 30 minutes as possible; however, a window of -5 minutes and +10 minutes is permitted (*i.e.*, infusion time is 25-40 minutes).

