7.4 Follow-Up Disease Assessment Schedule

The same imaging modality as used at prestudy for disease assessment (see [Section 5.1.c](#)) must be used throughout the study.

For CT imaging, iodinated contrast is recommended in addition to FDG for optimal relapse detection. If there is a contra-indication to iodine, non-contrast chest CT and MRI of abdomen/pelvis with gadolinium are acceptable body imaging alternatives. Extremity melanomas must be imaged using CT with intravenous contrast or MRI with and without gadolinium.

Neoadjuvant participants must undergo disease assessments after the 3rd pre-operative dose/before surgery (Weeks 7-12, timing per site discretion). Disease assessments then occur every 12 weeks thereafter until participant receives surgery or has progression of disease before surgery such that the participant cannot receive the planned surgery.

Following surgery, disease-free status must be documented within 42 days prior to step 3 registration, using the same modalities as prestudy. If the interval between scans and Adjuvant therapy exceeds 42 days, repeat imaging must be obtained.

Disease assessments will then continue every 12 weeks (+/- 2 weeks) until relapse or 2 years from randomization and timed from prior imaging. Participants who are still relapse-free will then have disease assessments performed every 6 months (\pm 4 weeks) until relapse or 5 years from randomization.

In the case of a variation in scan schedule due to early or missed or delayed scans, the subsequent scan is to be scheduled at the appropriate interval from the date of prior total body scan.

During treatment and follow-up (through year 5), brain MRI/CT must be **repeated annually (\pm 4 weeks)**; for years 6 through 10, brain MRI/CT to be performed annually as clinically indicated. If there is a gadolinium allergy, or MRI brain intolerable for the participant, CT with iodinated IV contrast is adequate brain imaging. Brain imaging is required for participants with progressive disease.

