 - j. Participants with primary melanoma of the head and neck or unknown primary with disease in the axilla will also require a neck CT.
 - k. Disease assessments by CT chest/abdomen/pelvis (or MRI if CT cannot be done), and neck CT as needed will be performed within 42 days (+/- 1 week) before surgery, and every 12 weeks (+/- 2 weeks) from the start of Adjuvant therapy until 2 years from randomization, then every 6 months (\pm 4 weeks) until 5 years from randomization, then follow for survival. In the case of a variation in scan schedule due to early or missed or delayed scans, the following scan is to be scheduled at the appropriate interval from the date of prior scan. If the interval between scans and Adjuvant therapy exceeds 42 days, repeat imaging must be obtained. The same imaging modality as used at prestudy for disease assessment should be used throughout the trial. If there is a contra-indication to iodine, non-contrast chest CT and MRI of abdomen/pelvis with gadolinium are acceptable body imaging alternatives. Extremity melanomas must be imaged using CT with intravenous contrast or MRI with and without gadolinium.

Note: PET-CT scans are NOT acceptable to establish eligibility.

(k. continued)

NOTE: If the disease assessment was completed within the last 42 days between the post-cycle 3 scan and registration for Step 3 (Adjuvant therapy), scans do not need to be repeated. If more than 42 days have elapsed between the post-cycle 3 scan and registration for Step 3 (Adjuvant therapy), scans must be repeated.

- l. During treatment and follow-up (through year 5), brain MRI/CT must be repeated annually (\pm 4 weeks); for years 6 through 10, brain MRI/CT to be performed annually as clinically indicated. If there is a gadolinium allergy, or MRI brain intolerable for the participant, CT with iodinated IV contrast is adequate brain imaging. Brain imaging is required for participants with progressive disease.
- m. If participant consents, submit specimens for banking as specified in [Section 15.2](#).
- n. Blood needs to be drawn prior to treatment.
- o. TSH (with a reflex to free T4) to be done at baseline on the same day of treatment (but prior to administration) and then as clinically indicated while on protocol treatment.

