- q. Neoadjuvant participants must undergo disease assessments and tumor measurements via RECIST 1.1 at baseline and after the 3rd pre-operative dose/before Surgery (Weeks 7-12, timing per site discretion). Disease assessments then occur every 12 weeks thereafter until 2 years from randomization, then every 6 months (\pm 4 weeks) until 5 years from randomization, then follow for survival. In the case of a variation in scan schedule due to early or missed or delayed scans, the following scan is to be scheduled at the appropriate interval from the date of prior total body scan. If the interval between scans and the start of Adjuvant therapy exceeds 42 days, repeat imaging must be obtained. The same imaging modality as used at prestudy for disease assessment should be used throughout the trial. If there is a contra-indication to iodine, non-contrast chest CT and MRI of abdomen/pelvis with gadolinium are acceptable body imaging alternatives. Extremity melanomas must be imaged using CT with intravenous contrast or MRI with and without gadolinium.
- t. History prior to each treatment initiation to include a menstrual, sexual and contraceptive use history, including date of last menstrual period (for women of childbearing potential) which will help determine the need for pregnancy testing. Similar questions regarding contraceptive use to be asked of men who are sexually active with women of childbearing potential. Height is only required at baseline.
- v. Participants with history of CHF or who are deemed at risk because of underlying cardiovascular disease or exposure to cardiotoxic drugs should have an ECHO prior to treatment and an ECHO and EKG at the start of each cycle, as clinically indicated. Participants who have evidence at baseline (or subsequently) of CHF, MI, cardiomyopathy, or myositis cardiac evaluation (NYHA I/II) should have additional consult by a cardiologist, including review of EKG, CPK, troponin, ECHO cardiogram, as clinically indicated.
- w. Neoadjuvant Arm: pembrolizumab (MK-3475) 200 mg flat dosing IV every 3 weeks for 3 doses followed by surgical resection. Post-operative dosing every 3 weeks x 15 doses (18 doses total).

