10.10 Event-Free Survival

Measured from date of randomization to date of first: documentation of progression that renders participant unable to receive planned protocol surgery, off protocol therapy for any reason without subsequent protocol surgery (with one exception noted below), failure to begin adjuvant therapy within 84 days after surgery, relapse after surgery or death due to any cause. Participants last known to be alive and event-free are censored at date of last contact. On both arms, all participants who do not register for adjuvant therapy (for whatever reason) will be assigned the event time of 84 days.

Patients treated on the neo-adjuvant arm who achieve an unconfirmed PR or CR (per RECIST 1.1) at the first protocol disease assessment and choose not to undergo protocol surgery will not be counted as an event if the PR or CR is confirmed prior to starting any non-protocol therapy other than pembrolizumab. Such patients will not have an event when not receiving protocol surgery, and their EFS will be measured from the date of randomization to the first of relapse or death due to any causes with patients last known to be alive without relapse censored at the date of last contact. All other patients who do not receive protocol surgery will be assigned the EFS event time of 84 days.

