10.11 Length of disease control

Measured from date of randomization to date of the first of the following events: progression such that the participant cannot receive protocol surgery, protocol surgery that does not render the participant disease-free, relapse after surgery that did render a participant disease-free, death due to any cause; participants last known to be alive without any of these events will be censored at the date of last contact.

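### Objective 1.2b asks for a between-arm comparison of disease control at 24 weeks, but Section 11.4 plans only log-rank and Cox comparisons over all follow-up

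*Combined protocol and SAP*

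**What the plan says.** Section 1.2b sets the objective: "To compare between arms overall survival (OS), disease control at 24 weeks", followed by locoregional control and number of doses.

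Section 10.11 defines a time-to-event variable. It runs from randomization to the first of progression that prevents protocol surgery, surgery that leaves disease, relapse, or death, and "participants last known to be alive without any of these events will be censored at the date of last contact". It contains no 24-week status or landmark.

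Section 11.4 states that "disease control will be estimated using the Kaplan-Meier method and compared between arms using log-rank tests and Cox regression models". It names no time point, truncation or 24-week contrast, and no other section supplies one.

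Scans are not anchored at 24 weeks from randomization:
- Section 7.4: "Disease assessments will then continue every 12 weeks (+/- 2 weeks) until relapse or 2 years from randomization and timed from prior imaging".
- Study calendar footnote k: "every 12 weeks (+/- 2 weeks) from the start of Adjuvant therapy".
- Study calendar footnote q, neoadjuvant arm: "after the 3rd pre-operative dose/before Surgery (Weeks 7-12, timing per site discretion", then every 12 weeks.

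Section 10.12 defines length of loco-regional control. It censors at death or at recurrence outside the primary site and the pre-defined nodal basins, whichever is first.

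**The concern.** The objective and the planned analysis target different quantities. A log-rank test or Cox model over all follow-up compares whole curves; it does not estimate a difference at week 24. The gap is more than wording. Section 11.2 says, for EFS, that hazards are not proportional and that the average hazard ratio drifts towards the null with longer follow-up. If disease control behaves alike (an assumption), the Cox summary depends on how long patients are followed and cannot stand in for a fixed-time answer.

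At stake is one secondary objective. It would be reported either without a prespecified between-arm result or with a contrast chosen after the data are seen.

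The loco-regional issue is separate and smaller. With competing events censored, one minus Kaplan-Meier is not the probability of loco-regional failure.

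**Working it through.** **Plan's own figure.** The documents give no sample size, power or significance level for disease control, so there is nothing to reproduce for it. As context, the primary test with 104 events, hazard ratio 0.64 and two-sided 15% gives Φ(√104/2 × |ln 0.64| − 1.44) = 79.8%, against 81% stated.

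**Inputs for an illustration.** The Section 11.2 EFS curves serve as a proxy, with 336 eligible patients (Section 11.3), or 168 per arm. The proxy is imperfect, and the direction of its error is unclear. EFS also counts going off therapy without surgery and "failure to begin adjuvant therapy within 84 days after surgery", which 10.11 does not; 10.11 counts surgery that leaves disease.

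**24-week values** (t = 168/365.25 = 0.46 years):
- Adjuvant: 0.6 + 0.4 × 2^(−0.46/2) = 94.1%, about 168 × 0.0589 = 10 events.
- Neoadjuvant: 0.7 + 0.3 × 2^(−0.46/2.5) = 96.4%, about 168 × 0.0359 = 6 events.
- Difference: 2.3 points.
- SE = √(0.9411 × 0.0589/168 + 0.9641 × 0.0359/168) = 0.0232; half-width 1.96 × 0.0232 = 4.5 points.
- Power: about 17% at two-sided 5% and 34% at 15%. The plan gives no level for secondary tests; 15% is its primary level.

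By comparison, a whole-curve log-rank test with 104 events and hazard ratio 0.64 has about 62% power at 5%. The two analyses differ in target and in operating characteristics.

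**Scan timing.** I take the preferred intervals and, as an assumption, the first neoadjuvant dose on the day of randomization. I also assume every event is found only at a scheduled scan, which makes the effect an upper bound for that schedule. Dates are nominal, ignoring the ±2-week window.

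- *Adjuvant arm.* Section 7.2 says participants "must be registered to Step 2 (Surgery) within 17 days (preferably within 14 days) after randomization", with surgery preferably within 14 days after that and adjuvant therapy preferably within 14 days of surgery. So surgery is at day 28 and adjuvant start at day 42. The first on-adjuvant scan is at day 42 + 84 = 126 (week 18) by footnote k. It is at days 112–126 if timed from a disease-free scan on days 28–42 (7.4).
- *Neoadjuvant arm.* The third dose is at day 42. Surgery is recommended within 3 weeks, so by day 63 (week 9), with adjuvant start at day 77. The scan is at day 77 + 84 = 161 (week 23) by footnote k, and at days 147–161 by 7.4. By footnote q the pre-operative scan falls in weeks 7–9, so the next is at weeks 19–21.

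Proxy values used: S_adj = 0.9597, 0.9549, 0.9526, 0.9479 and 0.9433 at days 112, 126, 133, 147 and 161. S_neo = 0.9712, 0.9683 and 0.9655 at days 133, 147 and 161.

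| Rule | Recorded difference (true 2.3 points) | Identical arms (adjuvant curve) |
|---|---|---|
| Footnote k in both arms | 0.9655 − 0.9549 = 1.1 | 0.9549 − 0.9433 = 1.2 |
| 7.4 in both arms | 0.9655 − 0.9597 = 0.6 to 0.9683 − 0.9549 = 1.3 | 1.2, from 0.9597 − 0.9479 or 0.9549 − 0.9433 |
| Footnote q (weeks 19–21) against adjuvant week 18 | 0.9683 − 0.9549 = 1.3 to 0.9712 − 0.9549 = 1.6 | 0.9549 − 0.9526 = 0.2 to 0.9549 − 0.9479 = 0.7 |

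In the 7.4 row, the recorded range lets the surgery-to-scan interval differ between arms; the identical-arms figure holds it equal. Overall, the recorded difference is about 0.6–1.6 points, and identical arms would differ by about 0.2–1.2 points, with the neoadjuvant arm looking worse.

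**Loco-regional estimate.** I assume proportional cause-specific hazards and a competing share c of one-third to two-thirds. One minus Kaplan-Meier is 1 − S^(1−c); the cumulative incidence is (1−c)(1−S). On the adjuvant proxy curve:
- 2 years, S = 0.800: excess 0.49, 0.56 and 0.50 points for c = 1/3, 1/2 and 2/3.
- 5 years, S = 0.671: excess 1.42, 1.64 and 1.49 points.

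**The case against.** The strongest reply is that 11.4 already commits to Kaplan-Meier curves, from which both 24-week values can be read, and already compares disease control between arms. What is missing is then one reporting sentence. The first part is right: each arm's estimate is available. But 1.2b says compare, and no difference or interval at week 24 is planned.

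A second reply is that a contrast with about 17% power is hardly worth having. That argues for reporting an estimate with an interval rather than a test, not for leaving the objective unanswered.

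On scan timing, a reader might infer from the weeks 7–12 window that the neoadjuvant follow-up scan runs to week 24, or that timing could shift the result by as much as the expected effect. The documents do not support either at preferred timing. Surgery is recommended within 3 weeks of the third dose, so a week-12 pre-operative scan implies delayed surgery. Physical examinations precede every 3-week cycle, and 10.11 also counts deaths and surgery that leaves disease, which do not depend on scan dates. Section 10.11 uses event dates, and 7.4 and the footnotes cover early, missed and delayed scans. An interval-censored analysis is therefore optional.

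On loco-regional control, the objection that 1.2b asks for a comparison, and that log-rank and Cox are valid for it, stands. The excess at 2 years is also small against a half-width of 1.96 × √(0.8 × 0.2/168) = about 6 points. Section 2.0 puts distant relapses above half of relapse events in Stage III, which makes the one-third share the less likely end; the excess hardly changes across the range.

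**Conclusion.** The mismatch holds on the text alone and needs no assumption: the objective names 24 weeks, and neither the definition nor the analysis does. It is a modest defect in a secondary objective.

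A reader might conclude that the planned log-rank and Cox analyses are wrong or that the trial's main conclusion is at risk. Neither follows. Both analyses are valid for length of disease control, and as cause-specific comparisons for loco-regional control, and the primary EFS test does not depend on them.

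The sizes above are illustrations. They rest on the EFS design curves standing in for disease control, on 168 per arm and, for scan timing, on preferred intervals with scheduled-scan detection only. They show that the 24-week contrast will be imprecise and somewhat sensitive to the arms' schedules. The 16% unresectability threshold in Section 11.5 triggers suspension of accrual; it is neither an expected rate nor a bound, so it supports no wider scenario.

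**What to change.** In Section 11.4, add for objective 1.2b the between-arm difference in Kaplan-Meier disease control at 24 weeks, with a 95% confidence interval from Greenwood or log-log standard errors, reported as an estimate. Keep log-rank and Cox for length of disease control. A sensitivity estimate treating scan-detected events as interval-censored is optional.

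For loco-regional control, report Aalen-Johansen cumulative incidence, with death and outside recurrence as competing events, alongside the planned log-rank and Cox.

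The cost is two or three sentences and a little programming, with no new data or procedures. The downside is that the 24-week difference will be imprecise and should not be read as a powered test.

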Dosing interruptions are permitted in the case of medical/surgical events or logistical reasons not related to study therapy (e.g., elective surgery, unrelated medical events, participant vacation, and/or holidays). Participants should be placed back on study therapy within 3 weeks of the scheduled interruption, unless otherwise discussed with the Study Chairs. The reason for interruption should be documented in the participant's study record.

All planned doses must be administered. Missed doses must be made up.

CLOSED EFFECTIVE 05/05/2022

d. **Arm 2: Pembrolizumab (MK-3475) Neoadjuvant Arm**

Step 1: RANDOMIZATION AND NEOADJUVANT THERAPY

Agent	Dose	Route	Schedule
MK-3475 (pembrolizumab)	200 mg over 30	IV for 3 doses minutes	Day 1, Q 3 weeks followed by surgical resection.

Participants will receive 3 doses of pre-operative (MK-3475) pembrolizumab. Administration of less than 3 doses of pre-operative pembrolizumab (MK-3475) may be allowed in cases of progressive disease requiring surgery or due to toxicity. This must be discussed with the Study Chair for approval. No additional doses of pre-operative pembrolizumab (MK-3475) treatment beyond 3 doses may be given.

Pembrolizumab (MK-3475) treatment should be administered after all procedures and assessments have been completed. Pembrolizumab (MK-3475) treatment may be administered up to 3 days before or after the protocol-specified Q 3 weeks due to administrative reasons.

Pembrolizumab (MK-3475) treatment will be administered on an outpatient basis.

Pembrolizumab (MK-3475) will be administered as a 30-minute IV infusion. Infusion timing should be as close to 30 minutes as possible; however, a window of -5 minutes and +10 minutes is permitted (*i.e.*, infusion time is 25-40 minutes).

Dosing interruptions are permitted in the case of medical / surgical events or logistical reasons not related to study therapy (e.g., elective surgery, unrelated medical events, participant vacation, and/or holidays). Participants should be placed back on study therapy within 3 weeks of the scheduled interruption, unless otherwise discussed with the Study Chairs. The reason for interruption should be documented in the participant's study record.

All planned doses must be administered. Missed doses must be made up.

Step 2: SURGERY:

Surgery should be arranged prior to Step 2 registration. It is recommended that participants undergo Surgery within 3 weeks after the last dose of pembrolizumab (MK-3475).

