Note: participants must be registered to Step 2 (Surgery) before surgery is performed.

If participants are unable to undergo Surgery by Week 12 due to development of irAE or an unrelated event such as intercurrent medical illness or life event, additional doses of pre-operative pembrolizumab (MK-3475) must be discussed with the Study Chair for approval with a plan to reschedule Surgery at the safest and earliest time point. **Inability to coordinate Surgery by Week 12 with the local surgeon is not an acceptable reason to administer additional doses of pembrolizumab (MK-3475).**

Step 3: ADJUVANT THERAPY

It is recommended that participants be registered to and initiate treatment on Step 3 (Adjuvant therapy) within 17 days (preferably within 14 days) after surgery. Radiation is allowed after surgery. However, interval between Surgery and start of Adjuvant therapy must not exceed 84 days.

Agent	Dose	Route	Schedule
MK-3475 (pembrolizumab)	200 mg	IV over 30 minutes	Q 3 weeks for 18 doses total (pre-operative doses + post-operative doses)

Pembrolizumab (MK-3475) is to be resumed after surgery and continued every 3 weeks x 15 doses for a total of 18 doses (neoadjuvant + adjuvant).

Pembrolizumab (MK-3475) treatment should be administered after all procedures and assessments have been completed. Pembrolizumab (MK-3475) treatment may be administered up to 3 days before or after the protocol-specified Q 3 weeks due to administrative reasons.

Pembrolizumab (MK-3475) treatment will be administered on an outpatient basis.

Pembrolizumab (MK-3475) will be administered as a 30-minute IV infusion. Infusion timing should be as close to 30 minutes as possible; however, a window of -5 minutes and +10 minutes is permitted (*i.e.*, infusion time is 25-40 minutes).

Dosing interruptions are permitted in the case of medical / surgical events or logistical reasons not related to study therapy (e.g., elective surgery, unrelated medical events, participant vacation, and/or holidays). Participants should be placed back on study therapy within 3 weeks of the scheduled interruption, unless otherwise discussed with the Study Chairs. The reason for interruption should be documented in the participant's study record.

All planned doses must be administered. Missed doses must be made up.

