11.3 Sample size re-design

Because accrual to the study has been slower than anticipated, it is expected that 100% of events may be reached before accrual to the study completes, and so the total sample size of the study will be adjusted as follows.

To account for the slower than anticipated accrual rate, a total of 336 eligible, randomized patients will be accrued. If up to 1.5% of patients are not eligible, up to 342 patients will be registered. With the same assumptions for EFS as in the original design, this design should have the same power as the original design using the same alpha. We expect to reach full events within 6 months of completing accrual.

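### Fisher's exact test is named for the number of doses (0 to 18) with no grouping; on the dose-by-dose table it ignores order and cannot show which arm received more

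*Combined protocol and SAP*

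**What the plan says.** Section 1.2b makes the "total number of pembrolizumab (MK-3475) doses received" one of the secondary comparisons between arms. Section 11.4 assigns the method: Fisher's "exact test will be used to compare the number of pembrolizumab (MK-3475) doses received". It gives no categories or cut-point, no significance level, no summary measure and no ordered test for this comparison.

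Section 7.2 sets the range of the count. The adjuvant arm is scheduled "Day 1, Q 3 weeks for 18 doses", all after surgery. The neoadjuvant arm is scheduled "Q 3 weeks for 18 doses total (pre-operative doses + post-operative doses"), and before surgery "Participants will receive 3 doses of pre-operative (MK-3475) pembrolizumab"; fewer than three are possible with approval. Section 10.10 foresees non-starters, since it assigns an EFS event time to a group that begins "On both arms, all participants who do not register for adjuvant therapy (for whatever reason"). Section 11.3 sets the current size: "a total of 336 eligible, randomized patients will be accrued".

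**The concern.** A dose count from 0 to 18 has up to 19 ordered values. Fisher's exact test treats table columns as unordered labels. If the count is tabulated dose by dose, the test asks whether the two distributions differ in any way, while the objective is a comparison of how many doses each arm received.

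Two things follow. A genuine shift in exposure may be missed, because the test spreads its power over every pattern of difference. And a significant result may reflect only where early leavers fall in the table. Someone who never starts adjuvant therapy has 0 doses on the adjuvant arm and typically about 3 on the neoadjuvant arm. A p-value from that table could not be read as more or less exposure on either arm. Because the grouping is not stated, the choice could also be made after the data are seen.

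**Working it through.** **No figure to reproduce.** The plan gives no power, effect size or dose distribution for this comparison. The dose distributions below are therefore assumptions.

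**Inputs from the plan.** 336 eligible participants (Section 11.3) randomized 1:1 (Section 6.0), so 336 / 2 = 168 per arm. Planned maximum of 18 doses on each arm (Section 7.2). No significance level is stated for this test; two-sided 5% is assumed. The two-sided 15% in Section 11.2 is for the primary EFS test.

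**Why order is ignored.** With fixed margins, the probability of a 2 x 19 table is proportional to the product over k of C(t_k, x_k), where t_k is the total with k doses and x_k the number of these on one arm. Relabelling the columns leaves the product, and so the p-value, unchanged.

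**Dose model.** With a constant chance h of stopping after each dose, P(X = k) = (1 - h)^(k-1) h for k = 1 to 17, P(X = 18) = (1 - h)^17, and the mean is [1 - (1 - h)^18] / h. For h = 0.04 the mean is (1 - 0.480) / 0.04 = 13.0 and P(18) = 0.96^17 = 0.50.

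**Step 1: pure shift.** Simulated power at 168 per arm, 600 trials per row. The last column is full-table Fisher divided by Wilcoxon.

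| h, two arms | Mean doses | Fisher, full table | Wilcoxon | Fisher, 18 vs <18 | Kept |
|---|---|---|---|---|---|
| 0.10 vs 0.07 | 8.5 vs 10.4 | 0.38 | 0.82 | 0.76 | 46% |
| 0.05 vs 0.03 | 12.1 vs 14.1 | 0.47 | 0.91 | 0.89 | 52% |
| 0.06 vs 0.035 | 11.2 vs 13.5 | 0.62 | 0.96 | 0.95 | 65% |
| 0.04 vs 0.02 | 13.0 vs 15.2 | 0.70 | 0.97 | 0.97 | 72% |
| 0.10 vs 0.06 | 8.5 vs 11.2 | 0.76 | 0.99 | 0.99 | 77% |

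With 5% at zero doses on both arms:

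| h, two arms | Fisher, full table | Wilcoxon | Fisher, 18 vs <18 | Kept |
|---|---|---|---|---|
| 0.03 vs 0.045 | 0.29 | 0.63 | 0.64 | 46% |
| 0.03 vs 0.05 | 0.50 | 0.86 | 0.88 | 58% |
| 0.04 vs 0.06 | 0.34 | 0.74 | 0.74 | 46% |

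The standard error is at most sqrt(0.25 / 600) = 0.02, and repeat runs of these rows differ by a few points. With equal distributions, Fisher rejected in 5% to 7% of trials and Wilcoxon in 5% to 6%, so both hold their level. At the original 250 per arm, the shifts in the first table keep between 0.61 / 0.92 = 66% and 0.94 / 1.00 = 94%.

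**Step 2: the schedule effect.** Assume 10% on each arm never start adjuvant therapy, at 0 doses on the adjuvant arm and 3 on the neoadjuvant arm. Give the other 90% the same h = 0.04 on both arms.

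- Adjuvant mean: 0.9 x 13.0 = 11.7.
- Neoadjuvant mean: 0.9 x 13.0 + 0.1 x 3 = 12.0.
- Share receiving all 18: 0.9 x 0.50 = 0.45 on both arms.
- Expected count at 0 doses: 0.10 x 168 = 16.8 against none.

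That one column drives the full-table test, which rejected in about 99% of trials. Wilcoxon rejected in about 5% (7.5% in a repeat run) and Fisher on 18 versus fewer in 4%.

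**Step 3: variant with early stopping risk removed.** If every neoadjuvant participant receives at least 3 doses and can stop only after that, the arms differ more. With 10% at 0 and at 3 doses:

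| h, adjuvant vs neoadjuvant | Mean doses | Fisher, full table | Wilcoxon | Fisher, 18 vs <18 |
|---|---|---|---|---|
| 0.03 vs 0.03 | 12.7 vs 13.8 | 0.99 | 0.29 | 0.10 |
| 0.05 vs 0.05 | 10.9 vs 12.4 | 0.99 | 0.52 | 0.13 |
| 0.03 vs 0.05 | 12.7 vs 12.4 | 1.00 | 0.12 | 0.46 |

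**The case against.** The strongest reply is that Fisher's test is normally used on categories, so the sentence may intend a grouped count, most naturally all 18 planned doses against fewer. Step 1 supports this: that version loses at most about 6 points under a shift and nothing visible in the rows with 5% at zero. It stands as a reading. But Section 11.4 does not state it, and the objective is the number of doses.

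A reader might infer that the plan throws away half the power. The documents do not support that as a general statement. It needs an uncollapsed table, a uniform shift, equal zero-dose fractions on both arms and a moderate effect at 168 per arm. Step 3 shows the order can reverse, with Fisher far ahead of Wilcoxon.

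A reader might also infer that the 99% in step 2 is an inflated false-positive rate. It is not. The two distributions do differ, at 0 and at 3 doses, and the test holds its level when they are equal. The fault is one of interpretation: the rejection says almost nothing about which arm received more.

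Finally, the rank test is not better against every alternative. In step 3 it had power of 0.29 and 0.52 where mean doses differed by 1.1 and 1.5. Moving to it gives up sensitivity to shape in exchange for an answer to the directional question.

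**Conclusion.** The point holds in a limited form. Section 11.4 names an unordered test for an ordered count and leaves the grouping unstated. On the dose-by-dose table, the result does not answer objective 1.2b. The size depends on assumptions that the plan does not supply: about 45% to 77% of rank-test power under pure shifts at 168 per arm and two-sided 5%; little or no loss if 18 versus fewer is meant; and near-certain rejection driven by the schedule if about 10% on each arm never start adjuvant therapy. The direction of the problem (missed shift or uninterpretable rejection) therefore cannot be fixed in advance. The stakes are modest: one secondary comparison with no stated power or decision rule. The primary EFS log-rank test is untouched.

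**What to change.** In Section 11.4, replace the sentence with one that:

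- compares the number of doses between arms with the Wilcoxon rank-sum test, or the van Elteren test if stratified by the LDH and stage factors of Section 6.0;
- reports the median or mean difference with its confidence interval, and states the significance level;
- keeps Fisher's exact test only for a pre-specified binary summary, the proportion receiving all 18 planned doses.

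The mean difference is the safer choice if completion is high: at h = 0.03, 0.97^17 = 0.60 of an arm receive all 18, so its median is already 18.

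The cost is a sentence or two. No new data are needed, since Section 14.3 already requires a treatment form after each cycle. The small downside is that the rank test is less sensitive to differences in the shape of the dose distribution; a table of dose counts by arm would show these descriptively.
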